1.31.3 ANALYSIS OF THE SECONDARY ENDPOINT(S)

Secondary endpoint is QOD score at 1 month and 3 months.

Placebo and NAC-treated groups will be compared. QOD (mean \pm sd) will be compared via two-tailed t-test.

QOD scores may range from 0-75. There are 25 quality of life questions, scored 0-3 each. A lower score implies more severe dysfunction.

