1.28 STATISTICAL HYPOTHESES

Primary Efficacy Endpoint(s):

To determine if early treatment with NAC after head injury results in improved olfactory function, compared to placebo. Type of comparison: superiority. Time period: 1 and 3 months post-enrollment.

Null hypothesis: There is no difference in SIT score with NAC treatment or placebo. Alternative hypothesis: NAC treatment results in improved SIT score.

• Secondary Efficacy Endpoint(s):

To assess olfactory-specific quality of life measure in treated versus placebo groups. Type of comparison: superiority. Time period: 1 and 3 months post-enrollment.

Null hypothesis: There is no difference in QOD score with NAC treatment or placebo. Alternative hypothesis: NAC treatment results in improved QOD score.

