- Anticipated impact of dropout rates, withdrawal, missing data, etc. on study power: to compensate for such issues, we have increased our sample size by 5 subjects per group.
- Secondary endpoint: We have included a secondary endpoint to measure quality of life via a
 validated questionnaire (QOD). We have no specific guides for mean or variance for the
 questionnaire in terms of possible NAC or placebo treatment, so no calculations are possible.
 Nonetheless, a simple questionnaire poses no cost or risk, such that we see no reason to not
 collect these data.

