1.31 STATISTICAL ANALYSES

General Approach

1.31.1

Data (SIT scores, QOD scores) will be presented as means with standard deviations, as well as range. Placebo and NAC-treated groups will be compared statistically, with p<0.05 considered significant, via two-tailed t-test. If data are not normally distributed, nonparametric testing or appropriate post-hoc corrections will be applied.

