1.31.2 ANALYSIS OF THE PRIMARY EFFICACY ENDPOINT(S)

Primary endpoint is SIT score at 1 month and 3 months.

Placebo and NAC-treated groups will be compared. SIT (mean ± sd) will be compared via two-tailed t-test.

SIT scores may range from 0-40, and normal scores are well-established. An assignment of normosmia, mild hyposmia, moderate hyposmia, severe hyposmia, anosmia, or probable malingering can be made based on SIT score.

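### The secondary QOD is set up as an unranked superiority comparison at two visits, each at p<0.05, with no link to the SIT result and no exploratory label, although no power calculation was possible for it

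*Combined protocol and SAP*

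**What the plan says.** Section 1.28 (Statistical Hypotheses) treats the QOD as a formal comparison: "To assess olfactory-specific quality of life measure in treated versus placebo groups. Type of comparison: superiority. Time period: 1 and 3 months post-enrollment". It states a null hypothesis and the alternative "NAC treatment results in improved QOD score".

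Section 1.31.1 (General Approach) covers both scales: "Data (SIT scores, QOD scores) will be presented as means with standard deviations, as well as range". It then sets one decision rule: "Placebo and NAC-treated groups will be compared statistically, with p<0.05 considered significant, via two-tailed t-test". Section 1.31.3 repeats the two visits for the QOD ("Secondary endpoint is QOD score at 1 month and 3 months") and again names the two-tailed t-test. It describes no combined or repeated-measures analysis.

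The only mention of a correction is in section 1.31.1: "If data are not normally distributed, nonparametric testing or appropriate post-hoc corrections will be applied". It is triggered by non-normal data and is not a multiplicity rule.

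Section 1.29 explains why the QOD has no sample-size basis: "We have no specific guides for mean or variance for the" questionnaire under NAC or placebo. It justifies collecting the data on the ground that a questionnaire is cheap and harmless. The exploratory entries, in the objectives table and in section 1.31.9, are both marked not applicable.

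**The concern.** The stated rationale for the QOD is that of an inexpensive extra measure. The stated analysis is that of a confirmatory endpoint with two chances of success. As written, a p-value below 0.05 at either visit supports a statement of superiority on quality of life, whether or not any SIT comparison succeeds.

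Two things are at stake. First, two undivided tests give more false positives than the nominal level of one test. Second, a chance QOD finding after a negative SIT result could be reported as a demonstrated benefit, when the trial was neither sized nor structured to demonstrate it. This concerns the secondary endpoint only. Naming a single primary SIT visit would leave the QOD tested twice at 0.05 and unconditionally.

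**Working it through.** **Inputs from the documents.** 30 per arm; SIT means 17 and 25 with ± 10 read as a standard deviation; alpha 0.05 and power 0.8 for the SIT (section 1.29); two-tailed t-tests at p<0.05 (section 1.31.1); QOD at two visits (sections 1.28 and 1.31.3).

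**Inputs not in the documents, so assumed.** Correlation between the 1- and 3-month scores: 0 to 0.9. Correlation between SIT and QOD: 0.3 to 0.5. Higher QOD is better (section 1.31.3), so a positive SIT–QOD correlation is the natural direction.

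**Step 1: the plan's own figure.** n per arm = 2(1.96 + 0.84)² × 10² / 8² ≈ 24.5, rounded up to 25. Adding the 5 per group for dropout gives 30, as stated. This rests on the SIT alone; no corresponding figure exists for the QOD.

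**Step 2: at least one significant QOD result, no true effect.** With independent visits:

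- either direction: 1 − 0.95² = 9.75%, against 5% for one test;
- favouring NAC: 1 − 0.975² = 4.94%, against 2.5% for one test.

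For correlated visits, a bivariate normal calculation gives:

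| Between-visit correlation | Either direction | Favouring NAC |
|---|---|---|
| 0 | 9.75% | 4.94% |
| 0.3 | 9.51% | 4.76% |
| 0.5 | 9.07% | 4.54% |
| 0.7 | 8.35% | 4.17% |
| 0.8 | 7.81% | 3.90% |
| 0.9 | 7.04% | 3.52% |

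Simulated t-tests with 30 per arm and 58 degrees of freedom agree closely (either direction: 9.0% at correlation 0.5, 7.0% at 0.9). The inflation over a single test runs from 7.04/5 = 1.4 to 9.75/5 ≈ 2.0, and the directional ratios are the same (3.52/2.5 = 1.4; 4.94/2.5 ≈ 2.0).

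**Step 3: false NAC-favouring QOD with neither SIT test significant.** Simulation over the assumed ranges gives about 2.7% to 4.3% of trials. Set against 3.5% to 4.9% in Step 2, that is 2.7/3.5 ≈ 77% to 4.3/4.9 ≈ 88% of the false QOD benefits. As a check on the upper end, if SIT and QOD were unrelated and the visits independent, the figure would be 4.94% × 0.95² ≈ 4.5%.

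**Step 4: what a rule would do.** Holm across the two QOD visits starts at 0.025. It brings the either-direction chance to 1 − 0.975² = 4.9% with independent visits, and to about 4.6% to 4.0% at between-visit correlations of 0.5 to 0.8. Testing the QOD only after a significant SIT result at one named visit (3 months in this calculation), then by Holm, brings it to about 0.25% to 0.73% when nothing works (SIT–QOD correlation 0 to 0.5).

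**The case against.** The QOD is called secondary throughout, the study is a 60-patient single-site Phase 2 trial, and section 1.29 openly says the QOD could not be powered. Nothing says that a QOD result would override the SIT. This stands, and it is why the point is minor. It does not remove the point, because a secondary label does not limit what section 1.28 allows to be claimed.

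The text also never says in so many words that there are two separate tests. That is a reading, though the natural one when no joint analysis is described.

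Three stronger readings are tempting and are not supported:

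- A reader might infer that the chance of falsely claiming benefit is well above 5%. The 7% to 10% counts significant results in either direction, including placebo better. The NAC-favouring figure stays just below 5%; its proper comparator is 2.5%.
- A reader might take the 0.05 in section 1.29 as a promised family-wise rate that the QOD breaks. It is the alpha for the SIT calculation, and no family-wise rate is stated for the QOD.
- A reader might hold that a QOD benefit without a SIT benefit is an error in itself. The objectives table gives olfactory quality of life its own objective, so such a result is possible and worth reporting. What is missing is a rule for how firmly it may be claimed.

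Finally, making the QOD conditional on the SIT is not immediately workable. Section 1.31.2 says "Primary endpoint is SIT score at 1 month and 3 months", so there is no single primary comparison to condition on.

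**Conclusion.** The point holds, as a minor one. The plan makes a formal superiority claim available at either of two QOD visits, at undivided p<0.05 and independently of the SIT, for a measure with no power basis. The excess is 1.4 to 2.0 times the error of one test, and roughly three quarters to nine tenths of false QOD benefits would arrive without SIT support. These figures rest on assumed correlations, a global null and 30 analysed per arm; the structural finding rests on the text alone. The issue is confined to how the secondary result may be interpreted.

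**What to change.** **Preferred change, which can be adopted on its own.**

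- Section 1.28: remove the QOD superiority hypothesis.
- Section 1.31.1: limit the p<0.05 significance rule to the SIT.
- Section 1.31.3: replace the t-test sentence with wording such as: *QOD at 1 and 3 months is exploratory. Results will be given as NAC-minus-placebo mean differences with 95% confidence intervals, with no claim of superiority.*
- Objectives table and section 1.31.9: align the exploratory entries, now marked not applicable.

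**Alternative, if a formal QOD test is wanted.** First name the single primary SIT comparison, or a rule for handling two. Then test the QOD only if that comparison is significant, with the two QOD visits in a pre-specified order or by Holm. The objectives table gives a reason for each visit and ranks neither, so the order is for the sponsor to choose.

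**Cost.** A few sentences of wording; no patients, visits or data. The downside is that a QOD result without SIT support could be reported only as exploratory.

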1.31.4 SAFETY ANALYSES

There is no formal safety endpoint being evaluated. AEs will be counted per event and will be presented as number of AEs and severity.

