1.21 DISCONTINUATION OF STUDY INTERVENTION

If a patient notes a possible adverse effect, such as allergic reaction to study medication, we will discontinue study medication. Any new clinically relevant finding will be reported as an adverse event (AE). Because the outpatient course of study medication is only 6 days, we will not restart study

medication in that short timeframe and instead will withdraw the patient from this study. Such patients will still be offered planned follow up and the planned outcome measures will still be collected.

The data to be collected at the time of study intervention discontinuation will include the following:

• Details of possible adverse event, and appropriate care as indicated (for example ER assessment).

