1.22 PARTICIPANT DISCONTINUATION/WITHDRAWAL FROM THE STUDY

Participants are free to withdraw from participation in the study at any time upon request.

An investigator may discontinue or withdraw a participant from the study for the following reasons:

- Pregnancy
- Significant study intervention non-compliance
- If any clinical adverse event (AE), laboratory abnormality, or other medical condition or situation occurs such that continued participation in the study would not be in the best interest of the participant
- If the participant meets an exclusion criterion (either newly developed or not previously recognized) that precludes further study participation

The reason for participant discontinuation or withdrawal from the study will be recorded on the NAC Case Report Form (CRF). Subjects who sign the informed consent form and are randomized but do not receive the study intervention may be replaced. Subjects who sign the informed consent form, and are randomized and receive the study intervention, and subsequently withdraw, or are withdrawn or discontinued from the study, will be replaced. Patients who do not complete the full course of study drug/placebo will be noted in the results tables, and they will not be included in the statistical analysis of outcome measures, since this is a simple comparison of SIT score between patients receiving a 1 week course of NAC versus placebo.

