1.26.4 TIME PERIOD AND FREQUENCY FOR EVENT ASSESSMENT AND FOLLOW-UP

The occurrence of an adverse event (AE) or serious adverse event (SAE) may come to the attention of study personnel during study visits and interviews of a study participant presenting for medical care, or upon review by a study monitor.

All AEs including local and systemic reactions not meeting the criteria for SAEs will be captured on the appropriate case report form (CRF). Information to be collected includes event description, time of onset, clinician's assessment of severity, relationship to study product (assessed only by those with the training and authority to make a diagnosis), and time of resolution/stabilization of the event. All AEs occurring while on study must be documented appropriately regardless of relationship. All AEs will be followed to adequate resolution.

Any medical condition that is present at the time that the participant is screened will be considered as baseline and not reported as an AE. However, if the study participant's condition deteriorates at any time during the study, it will be recorded as an AE.

Changes in the severity of an AE will be documented to allow an assessment of the duration of the event at each level of severity to be performed. AEs characterized as intermittent require documentation of onset and duration of each episode.

PI will record all reportable events with start dates occurring any time after informed consent is obtained until 7 (for non-serious AEs) or 30 days (for SAEs) after the last day of study participation. At each study visit, the investigator will inquire about the occurrence of AE/SAEs since the last visit. Events will be followed for outcome information until resolution or stabilization.

Adverse Event reporting will adhere to all established guidelines, as described below.

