1.30 POPULATIONS FOR ANALYSES

• Intention-to-Treat (ITT) Analysis Dataset (i.e., all randomized participants):

Placebo group (n=30) NAC treated group (n=30)

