1.31.8 TABULATION OF INDIVIDUAL PARTICIPANT DATA

A Table containing individual patient data will be included.

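### Adverse events are planned only as event counts, with no number or percent of participants affected, no denominator and no stated display by arm

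*Combined protocol and SAP*

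**What the plan says.** Section 1.31.4 is the whole safety analysis plan, and it has two sentences. The first is "There is no formal safety endpoint being evaluated". The second sets the unit: "AEs will be counted per event and will be presented as number of AEs and severity".

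Other sections bear on what those counts would contain:

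- **What is recorded (1.26.4).** "AEs characterized as intermittent require documentation of onset and duration of each episode". Changes in severity are documented too, and worsening of a condition present at screening becomes an AE. Collection runs from consent "until 7 (for non-serious AEs) or 30 days (for SAEs) after the last day of study participation".
- **Who is in each arm (1.30).** The only analysis set is headed "Intention-to-Treat (ITT) Analysis Dataset (i.e., all randomized participants", with 30 printed against each arm. No set of treated participants is defined.
- **What happens to withdrawals (1.21 and 1.22).** For a participant who stops study drug because of a possible adverse effect, the investigators "instead will withdraw the patient from this study", although follow-up is still offered. Participants who were dosed and "subsequently withdraw, or are withdrawn or discontinued from the study, will be replaced". Those randomized but never dosed may be replaced.
- **Individual data (1.31.8).** "A Table containing individual patient data will be included". The section does not say that AEs are in it.

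**The concern.** A reader of the results will want to know how many people on N-acetyl cysteine (NAC) and how many on placebo had an adverse event. The planned output does not answer that. Ten events may be ten people with one event each or one person with ten, and a total by severity does not distinguish them.

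The documents give some reason to expect several events per person. Section 1.6.1 lists headache and GI upset as possible NAC effects, and sections 1.6.2 and 1.9 name headache as a sequela of head injury. The risk sections rest the safety case largely on a previous study of the same regimen that reported no adverse events. A clear participant-level safety summary is therefore one of the more useful things this trial could add.

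There is also no stated denominator. Even if the totals are split by arm, they cannot be turned into a rate without knowing how many people were dosed, and under the replacement rule that number is not fixed at 30.

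**Working it through.** **1. The plan's own figure.** The documents state no AE rate. The one relevant number is the nominal denominator of 30 per arm. From section 1.29: difference 25 − 17 = 8, SD 10, two-sided alpha 0.05, power 0.80.

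n per arm = 2 × (1.960 + 0.842)² × 10² / 8² = 24.5, rounded up to 25. Adding the 5 per arm allowed for dropout gives 30, as stated.

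**2. Can event totals mislead?** All AE inputs here are assumptions, with 30 per arm. Event totals are compared by an exact 1:1 binomial calculation and participants by Fisher's exact test. Both serve only as a yardstick.

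| Assumed case | Events, NAC v placebo | Exact p, events | Participants, NAC v placebo | Fisher p |
|---|---|---|---|---|
| Difference suggested | 10+1+1 = 12 v 1+1+1 = 3 | 0.035 | 3/30 (10%) v 3/30 (10%) | 1.0 |
| Difference masked | 10×1 = 10 v 2×5 = 10 | 1.0 | 10/30 (33%) v 2/30 (7%) | 0.021 |

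First row: 2 × (455 + 105 + 15 + 1) / 2¹⁵ = 1152 / 32768 = 0.035. Second row: with 12 affected out of 60, twice the hypergeometric probability of 10 or more in one arm is 0.021.

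**3. How often, if there is no true difference?** Assume that 30% of participants are affected in both arms, that an affected person has 1 plus a geometric number of further events, and that the totals are read as if events were independent. In 20,000 simulated trials per row:

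| Mean events per affected person | Totals unequal at p<0.05 |
|---|---|
| 1 | about 1% |
| 1.2 | about 3% |
| 1.5 | about 8% |
| 2 | about 17% |
| 4 | about 39% |

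A participant-level Fisher test stays at about 3% throughout. A second assumed model, with a mean of 0.5 to 1.0 AEs per person, gives 3–4% when events are independent. It gives 8–21% (mean 0.5) or 14–34% (mean 1.0) when they cluster within people (negative binomial, k from 1.0 down to 0.25). The distortion comes entirely from repetition within a person.

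**4. Does the plan count repeats?** Section 1.26.4 requires each episode of an intermittent AE to be documented, and section 1.31.4 counts events. Neither says whether an intermittent AE with ten episodes is one event or ten. Both readings are open.

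**5. The denominator.** If w dosed participants in an arm are withdrawn and replaced until 30 remain, the number dosed is 30 + w. For an assumed w of 0 to 5, ten affected people are 10/30 = 33% down to 10/35 = 29%. The effect is modest, but the plan does not say which denominator applies.

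**The case against.** The strongest reply is that nothing inferential depends on this. The plan disclaims a formal safety endpoint and AE reporting is descriptive, so there is no nominal 5% to inflate. That stands. The 17% and 39% above are not error rates of the trial, and they rest on assumed repetition. With one event per affected person the figure is about 1%.

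It can also be said that section 1.26.4 reads most naturally as one AE with several episodes recorded under it. A recurrent headache would then count once, and much of the repetition would disappear. That is a fair reading, but the plan does not state it, and one person can still have several different AEs.

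Three stronger inferences are tempting, and the documents do not support them:

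- **That participants withdrawn for AEs fall outside the only defined population.** They do not. The set in 1.30 is all randomized participants. Section 1.22 removes people with an incomplete course from the outcome analysis only and has them noted in the results tables. No section drops them from AE reporting.
- **That the trial cannot state the proportion affected.** It can. AEs are recorded for each participant on the case report form. Section 1.31.4 simply does not commit to reporting the proportion.
- **That both headache and GI upset recur after head injury.** The documents name headache as a sequela, but nothing says that GI upset recurs. Headache already present at screening counts only if it worsens.

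**Conclusion.** The concern holds as a gap in the planned display. Section 1.31.4 fixes the event as the only unit, and no other section supplies a participant-level AE count, a treated denominator or a by-arm layout. Event totals can then suggest or mask a difference in the number of people affected, as the two assumed examples show.

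The size cannot be derived from the documents, because they give no AE rates. On the assumptions above, it runs from negligible with one event per affected person to substantial with a mean of two or more. It affects a descriptive safety comparison and has no bearing on the primary analysis or its type I error rate. This is a minor point, worth making because the remedy is almost free.

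**What to change.** Rewrite section 1.31.4 as follows.

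- Report by arm, among all participants who received any dose of study drug or placebo, including those later withdrawn or replaced, and state the number dosed in each arm.
- Give the number and percent of participants with at least one AE and with at least one serious AE, each person counted once. Break these down by worst severity and by relatedness, with exact 95% confidence intervals.
- Keep the event count as a supplementary column, and state whether repeat episodes of an intermittent AE count once or separately.

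Section 1.30 should define this treated set alongside the existing one and make clear that 30 per arm is a target that replacement can exceed.

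The cost is a few sentences and one table. Section 1.26.4 already requires the onset, severity and relatedness of each AE on the case report form, so no new data are needed. Keeping the event counts means that no information is lost.

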1.6 RISK/BENEFIT ASSESSMENT

1.6.1 KNOWN POTENTIAL RISKS

Risks from medication: NAC is FDA approved, with a forty-year safety history. It is widely used for nebulized delivery to the lower airways for its mucolytic effects (Mucomyst). Otolaryngologists have prescribed NAC off-label as a topical nasal medication for years for certain chronic rhinosinusitis patients for it mucolytic effects, with no safety concerns reported. It also has a long history of systemic oral administration safely. It is used at high dose orally in emergency departments for acetaminophen overdose, to prevent hepatotoxicity. Known side effects reported from nebulized pulmonary delivery include some patients reporting a noticeable odor. Other possible side effects might include local irritation; however it has been used widely in the lower airways and via tracheostomy stoma without irritation. There are rare reports of bronchospasm reactions to NAC delivered to the lower airways via nebulizer; these typically respond to bronchodilators (albuterol). Loading doses for FDA-approved oral administration of NAC are about 55 ml of 20% NAC solution (≈10 g), and our study patients will receive a 4 g loading dose, much lower. Importantly, a recent published study using the identical oral NAC regimen proposed here reported no adverse events or treatment side effects³. NAC can cause headache or potentiate effects of nitroglycerine or isosorbide. It may alter levels of homocysteine. It may potentiate the effects of certain immunosuppressants, such as cyclophosphamide or azathioprine. It can cause GI upset.

Other risks: There is no economic risk, as we will supply the study medication. The pre-study work up and care is the trauma standard-of-care, unchanged, and is no different for patients choosing or not choosing to participate in this study. Psychologically, there is the risk of disappointment from possible lack of improvement or from treatment with placebo. However, the current standard-of-care is **no treatment**, so we will council patients regarding this.

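### The planned safety summary shows only AE counts and severity, so it could not show whether GI upset or headache was more frequent on NAC

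*Combined protocol and SAP*

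**What the plan says.** Section 1.31.4 is the whole of the planned safety analysis. It states "There is no formal safety endpoint being evaluated" and then that AEs are counted event by event and "will be presented as number of AEs and severity". It names no treatment arm, event type, analysis period, relationship or number of participants affected.

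Section 1.26.4 collects much more: "Information to be collected includes event description, time of onset, clinician's assessment of severity, relationship to study product", and the time of resolution. Reportable events are those starting "any time after informed consent is obtained until 7 (for non-serious AEs) or 30 days (for SAEs) after the last day of study participation". The same section treats a condition present at screening as baseline, so it becomes an AE only if it deteriorates. Section 1.26.3.2 requires a relatedness grade for every AE.

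On expected effects, section 1.6.1 says of NAC "It can cause GI upset" and also lists headache. It mentions bronchospasm only as rare reports with nebulized delivery, whereas this trial gives NAC by mouth. Section 1.9 counts headache among the common consequences of TBI. Under 1.16.2 and 1.19 the course is a loading dose before discharge and six further days.

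**The concern.** The information needed to interpret an adverse event in this trial is what it was, when it started relative to dosing, and whether it was judged related. All three are recorded, but the only planned summary does not call for them. Exposure lasts one week and recording lasts three months or more, in patients recovering from head injury. A count over all types and the whole window mixes possible drug effects with later events that the drug is unlikely to have caused. For headache, the drug and the injury can produce the same symptom.

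At stake is the trial's safety statement about this regimen after head injury. The risk–benefit argument (1.6.1, 1.6.3, 1.25) leans on one earlier study of the same regimen that reported no adverse events. This trial could check that in its own population, but a count by severity alone would not do so. Counting participants instead of events would not cure the problem if types and periods were still combined.

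**Working it through.** **1. Fields collected against fields reported**

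| Item | Recorded (1.26.4, 1.26.3.2) | Named in 1.31.4 |
|---|---|---|
| Number of events | yes | yes |
| Severity | yes | yes |
| Event description | yes | no |
| Time of onset | yes | no |
| Relationship | yes | no |
| Treatment arm | known after unblinding | no |
| Participants affected | derivable | no |

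**2. Share of the recording window spent on drug**

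The plan states no figure for the safety summary, so there is none to reproduce. Inputs are 7 dosing days (Day 0 plus 6 days) and a tail of 7 days for non-serious AEs or 30 for SAEs. The last visit is taken at day 90 if it falls at 3 months (1.1, 1.15), or at day 120 ± 21 if it follows the Schedule of Activities (Month 4 ± 3 weeks). These two timings need reconciling, because the last visit sets the AE window.

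Share = 7 / (last visit day + 1 + tail), counting from Day 0.

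| Last visit | Non-serious AEs | SAEs |
|---|---|---|
| Day 90 | 7/98 = 7.1% | 7/121 = 5.8% |
| Day 99 | 7/107 = 6.5% | 7/130 = 5.4% |
| Day 120 | 7/128 = 5.5% | 7/151 = 4.6% |
| Day 141 | 7/149 = 4.7% | 7/172 = 4.1% |

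For non-serious AEs the range is 4.7–7.1%. Up to two days between consent and first dose (consent is in the Day −2 to 0 column) barely change this.

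**3. What dilution could look like (assumed rates only)**

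The documents give no AE rates, so this step shows direction, not size. Assume 30 participants per arm (1.29), 2 background AEs per participant in each arm over 98 days (60 per arm), and 0.3 extra AEs per NAC participant during dosing (9 events).

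- Whole window: 60 against 69, ratio 69/60 = 1.15.
- Dosing week, background spread evenly: 60 × 7/98 = 4.3 against 13.3, ratio 3.1.
- Dosing week, 25% of background falling there: 15 against 24, ratio 1.6.
- Dosing week, 50% of background falling there: 30 against 39, ratio 1.3.

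The onset split gains most if background events are evenly spread and little if they cluster early. The documents support neither pattern. If events do cluster early, the split by event type has to do more of the work.

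**4. Can the planned table answer the question?**

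To see whether GI upset was more frequent on NAC, a reader needs GI events by arm. To judge headache, the reader also needs onset and preferably relationship. A table of event number by severity supplies none of these, whatever the background rate.

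**The case against.** The strongest reply is that 1.31.4 is silent rather than restrictive. It does not forbid a breakdown, and the window in 1.26.4 governs recording, not analysis. A serious harm would not go unseen: 1.26.6 requires a causality assessment for every SAE, 1.21 records the details when a possible adverse effect stops treatment, and 1.31.8 promises an individual data table. Because the fields are collected, a fuller table could be made later without loss of data. All of this stands, and it limits the point to what is planned. It does not remove it. None of these provisions is a between-arm comparison of the listed effects, the content of the 1.31.8 table is unspecified, and a breakdown chosen after unblinding is weaker than one written beforehand.

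A reader might infer two stronger claims:

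- That NAC's known harms will never be reported. The provisions just listed contradict this, and bronchospasm is documented only for nebulized use.
- That injury events will swamp any drug effect. No rates are given, and symptoms present at screening are not AEs unless they worsen. Only new or worsening symptoms could dilute the count.

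Pre-dose events are also a small matter. The schedule marks AE review from Day 0, and at the rates assumed above two extra days would add about 60 × 2/99 = 1.2 events per arm.

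Finally, the plan tests no safety hypothesis, so the chance of reaching p<0.05 on AE counts is not a fair measure of either the present table or the proposed one. Under 1.22, non-completers are left out of the outcome analysis, but the text does not say that they are left out of AE counts.

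**Conclusion.** The concern holds as a gap in the planned presentation. A safety table built as 1.31.4 is written could not show whether a listed effect such as GI upset or headache was more frequent on NAC, although the data to show it are collected. The firm figure is that dosing takes up about 5–7% of the non-serious AE window (4.7–7.1%, depending on which last-visit timing applies). That rests only on the documents' schedule.

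The degree of dilution is not established. The ratios in the working depend on assumed rates and on how background events are spread over time, and the conclusion does not rest on them. The efficacy analysis is unaffected. The change should be made before unblinding, but it concerns descriptive reporting and is not a flaw in the design.

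**What to change.** Rewrite 1.31.4 so that AEs are tabulated descriptively:

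- by arm, giving both events and participants with at least one event;
- by event type, with separate lines for GI upset, headache and allergic reaction/bronchospasm, noting that 1.6.1 documents bronchospasm only for nebulized use;
- by onset period: loading dose to the day after the last dose, and later, with any pre-dose events listed separately;
- with severity, relationship and seriousness shown;
- in everyone who took at least the loading dose, including those later withdrawn or replaced under 1.21 and 1.22. Section 1.30 names only an ITT set, so this safety set should be stated.

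Reconcile the 3-month and Month 4 timings of the last visit so that the AE window is fixed. No significance test is needed. If a dilution example is kept in the plan, label its rates as assumed and as dependent on evenly spread background events.

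The cost is SAP wording and one or two extra tables from fields already on the CRF. The downside is small cell counts per event type, which should be read descriptively.
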